7.2 General Study Procedures

Any blood sample collected according to the Schedule of Assessments (Table 2 and Table 3) may be analyzed for any of the tests outlined in the protocol and for any tests necessary to ensure subject safety. This includes testing to ensure analytical methods produce reliable and valid data throughout the course of the study. This may also include, but is not limited to, investigation of unexpected results, incurred sample reanalysis, and analyses for method transfer and comparability.

Throughout the study, the permitted time windows for scheduled assessments will be as follows:

- +4 day for Day 1 For Non Randomized (PACAP-38 Only) Dose Selection Subjects Only
- + 4 day for Day 8 for Randomized (AMG 334 or Placebo) Subjects
- ± 30 minutes for Headache Questionnaire
- ± 3 days for Days 29, Day 57 and EOS (Day 8 for Non Randomized (PACAP-38 Only) Dose Selection Subjects and Day 85 for Randomized (AMG 334 or Placebo) Subjects)

If informed consent is provided by the subject, Amgen may do additional testing on remaining samples (ie, residual and back-up) to investigate and better understand neurological disorders, the dose response and/or prediction of response to AMG 334, characterize antibody response, and characterize aspects of the molecule. Results from this analysis will be documented and maintained, but may not be reported as part of this study.

Additional procedures deemed necessary as part of standard of care or as required by local laws and regulations may be performed at the Investigator's discretion.

7.2.1 Informed Consent

Before any study-related screening or baseline procedure can be completed, a subject must sign and date the IRB/IEC-approved ICF. After informed consent has been obtained, all screening procedures and tests establishing eligibility will be performed. Screening procedures are summarized in the Schedule of Assessments (Table 2 and Table 3).

7.2.2 Screening and Day -1

After informed consent is obtained, all screening procedures will be performed between Day -21 and Day -1 at the time points designated in the Schedule of Assessments

(Table 2 and Table 3). Study eligibility must be met per inclusion/exclusion criteria prior to enrollment.

7.2.3 Subject Residency

7.2.3.1 Non Randomized (PACAP-38 Only) Dose Selection Subjects

After eligibility for enrollment is determined, subjects will be admitted to the research facility on study Day 1 and will receive PACAP-38 dose. Subject will remain in residency for 24 hours post PACAP-38 infusion. After discharge from residency, subjects will return to the research facility on Day 8 for an EOS visit (see Schedule of Assessments Table 3).

7.2.3.2 Randomized (AMG 334 or Placebo) Subjects

Subjects will be admitted to the research facility on study Day 8 and will receive PACAP-38 dose. Subject will remain in residency for 24 hours post PACAP-38 infusion. After discharge from residency, subjects will return to the research facility on an outpatient basis for scheduled study procedures, including blood draws for PK assessments, safety laboratory tests, and other assessments according to the Schedule of Assessments (Table 2).

7.2.4 Treatment

Treatment begins when the first dose of protocol-required therapies is administered to a subject. The treatment procedures are to be completed during the Treatment Visits at time points designated in the Schedule of Assessments (Section 7.1).

If any subject stops treatment (eg, due to an adverse event), the subject will be asked to continue to complete protocol-required visits for safety monitoring as determined by the Principal Investigator in consultation with the Amgen Medical Monitor and Amgen Global Safety Officer.

When multiple post dose procedures are required to be conducted at the same nominal time point, the following order of precedence will be used: (1) vital signs, (2) ECGs, (3) PK sample collection.

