3. EXPERIMENTAL PLAN

3.1 Study Design

This is a randomized, double-blind, placebo-controlled, parallel-group study in subjects with episodic migraines. This study will evaluate the efficacy of AMG 334 as measured by inhibition of PACAP-38 induced migraine-like attacks after a single dose of AMG 334. Migraine-like attacks (MLA) will be defined as attacks fulfilling one of the two criteria:

(1) Headache fulfilling criteria C and D for migraine without aura (IHS 2004)

- C. Headache has at least two of the following characteristics:
 - unilateral location
 - pulsating quality
 - moderate or severe pain intensity (≥ 4 on headache questionnaire)
 - aggravation by or causing avoidance of routine physical activity

D. During headache at least one of the following:

- nausea and/or vomiting
- photophobia and phonophobia

(2) Headache described as mimicking usual migraine attack treated with triptan.

Part A: PACAP-38 Dose Selection Phase: There are a number of published clinical studies in which pituitary adenylate cyclase-activating polypeptide-38 (PACAP-38) was used to trigger MLA in migraneurs (Schytz et al, Brain 2009; Amin et al, Cephalagia 2011; Amin, Brain 2014). In those studies, 10 pmol/kg/min over 20 minutes (total dose 200 pmol/kg) was administered. Approximately 90% of migraineurs experienced a headache and approximately 66% of the same migraineurs experienced MLA with a median time of headache onset of 4 hours, though the half-life of PACAP-38 is only 3.5 minutes. As PACAP-38 is involved in various biological processes, including sensory processing, vasodilation, inflammation, and nociceptive transmission (Dickinson et al., 1999; Vaudry et al., 2000), nearly all healthy subjects and migraineurs also experienced the expected adverse events of flushing and heat sensation, along with a transient elevation in heart rate and blood pressure (Birk et al, Regulatory Peptides 2007; Schytz et al, Brain 2009; Amin et al, Cephalagia 2011; Amin, Brain 2014) (see Investigator Brochure for details).

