7.2.10 Vital Signs

The following measurements must be performed: systolic/diastolic blood pressure, heart rate, respiratory rate, and temperature. The position selected for a subject should be the same that is used throughout the study and documented on the vital sign eCRF. Record all measurements on the vital signs eCRF. The temperature location selected for a subject should be the same that is used throughout the study and documented on the vital signs eCRF. Rectal temperature will be collected at the time points designated in Table 2 and Table 3. Vital signs (blood pressure, heart rate, respiratory rate, and temperature) will be recorded by the principal investigator or designee at time points specified in the Schedule of Assessments (Table 2 and Table 3).

Blood pressure will be measured in the following manner:

- Subjects should be lying in a semi-recumbent position quietly and comfortably for at least 5 minutes. The upper arm should be bare without constrictive clothing and supported at heart level.
- Three consecutive measurements separated by approximately 5 minutes must be taken to establish baseline (ie, pre-dose) systolic/diastolic blood pressure. The mean of the three measurements should be recorded.
- Any clinically significant decrease in blood pressure readings must be confirmed with three consecutive measurements taken approximately 5 minutes apart. The mean of the three measurements should be recorded.
- Caffeine and exercise should be avoided for at least 30 minutes prior to measurement.
- An appropriately sized cuff (cuff bladder encircling at least 80 percent of the arm) should be used to ensure accuracy. At least 2 measurements should be made and the average recorded.
- Neither the subject nor the observer (measurer) should talk during measurement.

Subjects should be lying in a semi-recumbent position quietly and comfortably for at least 5 minutes for respiration and heart rate assessments. Respiration will be assessed by a full minute count. Abnormal measurements may be repeated upon investigator discretion. Record all measurements on the vital signs eCRF.

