7.2.15 Electrocardiograms

During the study, 12-lead electrocardiograms (henceforth referred to as electrocardiogram or ECG) will be performed at the time points indicated in the Schedules of Assessments (Table 2 and Table 3).

The subject must be in supine position in a rested and calm state for at least 5 minutes before ECG assessment is conducted. If the subject is unable to be in the supine position, the subject should be in most recumbent position as possible.

At Screening, ECGs will be performed in a standardized method, in triplicate, and approximately 30 seconds apart, prior to blood draws or other invasive procedures. From Day 1 to EOS visit, ECGs will be performed as a single electrocardiogram. Each ECG must include the following measurements: QRS, QT, QTc, RR, and PR intervals.

The Principal Investigator or designated site physician will review all ECGs. Once signed, the original ECG tracing will be retained with the subject's source documents. At the request of the sponsor, a copy of the original ECG will be made available to Amgen.

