10.5.3.3 Pharmacokinetic Endpoints

Serum AMG 334 concentrations will be determined using a validated assay. Individual serum concentration-time plots for AMG 334 will be presented for each subject as well as mean concentration-time plots for each treatment group. PK parameters $C_{1 hour}$, and AUC_{84d} will be estimated using either compartmental (eg, PK modeling) or non-compartmental methods. Actual dosing and sampling times will be used for calculation of PK parameters. Summary statistics will be generated for each PK parameter for each treatment group. The PK concentration analysis set will be used for these analyses.

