10.1 General Principles

Unless otherwise stated, data from PACAP-38 responders who go on to be randomized and receive IP will be summarized. Data from PACAP-38 non-responders, and data from

Statistical Analysis Plan: 20140207

Date: 17 May 2017 Page 22

PACAP-38 responders that do not receive IP, will not be included in the summaries, but will be reviewed.

Unless otherwise specified, data will be summarized using the safety analysis set, by actual treatment group (AMG 334 or Placebo).

Descriptive statistics will be provided for selected demographics, safety and PK data. Descriptive statistics on continuous measurements will include means, medians, standard deviations (and standard errors for post-baseline data), quartiles, and ranges, while categorical data will be summarized using frequency counts and percentages. Where statistical models are applied to the data, estimates of the differences/ratios, confidence intervals and corresponding p-values will be presented, as applicable. However, these are for descriptive and illustrative purposes only and to aid interpretation of the data; no formal statistical hypothesis testing will be performed.

When data are summarized by time, the values recorded against the scheduled time points, including any time windows specified in the protocol will be used.

When assessing minimum/maximum increases or decreases over the study, all assessments, including unscheduled assessments will be used.

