10.7.4 Plasma Concentration of PACAP-38 and CGRP

Summary statistics will be generated for plasma PACAP-38 and CGRP levels pre/post dosing with PACAP-38. Summaries will be produced by treatment group for the second dose of PACAP-38 (ie., the dose administered after administration of IP).

Statistical Analysis Plan: 20140207

Date: 17 May 2017 Page 26

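### PACAP-38 levels are to be summarised by scheduled time although the peptide halves every 3.5 minutes; they should be summarised by actual minutes since the end of infusion

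*Protocol*

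**What the plan says.** **Order of procedures.** For post-dose procedures at one nominal time, Protocol 7.2.4 states that "the following order of precedence will be used: (1) vital signs, (2) ECGs, (3) PK sample collection".

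**Schedule.** In Protocol Table 2, PACAP-38 plasma is drawn on Day 8 before dosing and at 0.25 h and 0.5 h. Vital signs fall at both post-dose times; the ECG falls at 0.5 h only. AMG 334 serum PK and PACAP-38 plasma are separate rows.

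**Time the procedures take.** Protocol 7.2.10 asks for at least two averaged blood-pressure readings and a full-minute respiration count. A clinically significant fall in pressure "must be confirmed with three consecutive measurements taken approximately 5 minutes apart". For the ECG, Protocol 7.2.15 adds: "The subject must be in supine position in a rested and calm state for at least 5 minutes before ECG assessment is conducted".

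**Half-life.** Protocol 3.1 notes a median headache onset of 4 hours, "though the half-life of PACAP-38 is only 3.5 minutes".

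**Windows.** The only within-day window listed in Protocol 7.2 is 30 minutes either side for the headache questionnaire. A Table 2 footnote gives flexible timing to a Day 8 AMG 334 sample. Nothing is given for PACAP-38 plasma.

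**Analysis.** For data shown over time, SAP 10.1 states that "the values recorded against the scheduled time points, including any time windows specified in the protocol will be used". SAP 10.7.4 states: "Summary statistics will be generated for plasma PACAP-38 and CGRP levels pre/post dosing with PACAP-38", by treatment group for the dose given after investigational product. The rule "Actual dosing and sampling times will be used for calculation of PK parameters" stands in Protocol 10.5.3.3 and again in SAP 10.6.3. Both sections concern AMG 334 only.

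**The concern.** Actual times are specified for a monoclonal antibody whose exposure is followed over 84 days, and not for a peptide that loses half its level every 3.5 minutes. For the antibody, a few minutes hardly matter. For the peptide, two subjects with identical exposure can differ several-fold because one was drawn a few minutes after the other, and a table headed 0.25 h does not show this.

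PACAP-38 levels serve a stated exploratory objective. They are also the only planned measurement of the challenge agent in the subject's blood. That has some weight here, because the sponsor reformulated PACAP-38 after estimating that about 50% of the peptide may have been lost to surface binding in the published studies. A summary in which late draws look like low exposure would serve that purpose poorly.

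**Working it through.** The plan gives no figure of its own on this point, so there is none to reproduce.

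**Inputs**
- Half-life 3.5 min (Protocol 3.1), so k = ln 2 / 3.5 = 0.198 per min.
- Nominal draws at 15 and 30 min (Protocol Table 2).
- Infusion length: the Part B dose is chosen after Part A. Infusions of 5, 7.5, 10 and 11.5 min are taken from Protocol 6.3.1.1.
- Assumption: first-order decline of the infused peptide. Any endogenous level is left out.

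**Step 1: effect of a late draw.** Fraction left = 2^(−d/3.5) for a delay of d minutes.

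| Delay (min) | Fraction left | Reads low by |
|---|---|---|
| 1 | 82% | 18% |
| 2 | 67% | 33% |
| 3 | 55% | 45% |
| 5 | 37% | 63% |
| 10 | 14% | 86% |

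Ten minutes is the span of three readings 5 minutes apart (2 × 5). It would arise only after a clinically significant fall in pressure, and only if the draw waited for the confirmation.

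**Step 2: what is left when the draw is on time.** The sections cited do not say whether 0.25 h and 0.5 h run from infusion start or end. As a percentage of the end-of-infusion level:

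| Infusion (min) | 0.25 h from start | 0.25 h from end | 0.5 h from start | 0.5 h from end |
|---|---|---|---|---|
| 5 | 14% | 5.1% | 0.7% | 0.26% |
| 7.5 | 23% | 5.1% | 1.2% | 0.26% |
| 10 | 37% | 5.1% | 1.9% | 0.26% |
| 11.5 | 50% | 5.1% | 2.6% | 0.26% |

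For a 10-minute infusion the two clocks differ by 2^(10/3.5) = 7.25-fold; for 11.5 minutes, by 2^(11.5/3.5) = 9.75-fold. At 0.5 h at most about 2.6% remains on either clock, so the point rests on the 0.25 h sample.

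**Step 3: can timing dominate the spread?** The delay variance on the log scale is (k × SD of delay)². The between-subject variance is ln(1 + CV²). Neither the SD of delay nor the CV is in the documents, so both are assumed. For an SD of 2 min and a CV of 50%: (0.198 × 2)² = 0.157, ln 1.25 = 0.223, share due to delay = 0.157 / 0.380 = 41%.

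| SD of delay (min) | CV 30% | CV 50% | CV 80% |
|---|---|---|---|
| 1 | 31% | 15% | 7% |
| 2 | 65% | 41% | 24% |
| 3 | 80% | 61% | 42% |
| 5 | 92% | 81% | 66% |

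Delay makes up more than half of the log variance only if its SD exceeds √ln(1 + CV²) / k, which is 1.48, 2.39 or 3.55 min at a CV of 30%, 50% or 80%.

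**The case against.** **No delay is documented.** Section 7.2.4 fixes an order, not a start time, so vital signs could begin before the nominal time and the draw could still be punctual. This stands. A reader might infer that the PACAP-38 summaries mostly reflect sampling delay. The documents do not support that: over the assumed values in Step 3 the share runs from 7% to 92%.

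**The order may not cover these samples.** Section 7.2.4 speaks of PK samples, Table 2 lists PACAP-38 plasma apart from AMG 334 PK, and the PK endpoints elsewhere concern AMG 334. This also stands. It does not rescue the nominal-time summary: if the order does not apply, the position of the draw is simply unstated.

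**The ECG adds little.** None is scheduled at 0.25 h. Protocol 6.3.1.1 keeps subjects supine for about an hour after PACAP-38, so the rest period need not add time. I accept this and leave the ECG out of the argument.

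**A bias between arms.** A reader might infer that confirmatory readings delay placebo draws more, because AMG 334 blunts a fall in pressure. Nothing in the documents says that it does, and a delay common to both arms lowers both by the same factor.

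**Not the only exposure check.** Protocol 6.3.1.1 records the quantity, volume, concentration and start and stop times of PACAP-38, and SAP 10.10 lists administration for every subject. Plasma is the only measurement in the subject, not the only check on the challenge given.

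**Unseen sources.** Collection instructions sit in a separate manual (Protocol 7.2.26), which may set draw times. The SAP follows Protocol Amendment 4, whereas the protocol supplied is Amendment 3. Either may already cover part of this. Neither would alter the SAP's own rule to summarise by scheduled time.

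**Conclusion.** The point holds in a limited form. A nominal-time summary suits a peptide with a 3.5-minute half-life only if draws are tightly timed, and nothing in the supplied text ensures that. A draw 2 to 5 minutes late reads 33% to 63% low, chiefly relevant at 0.25 h. The undefined time zero adds a 7- to 10-fold uncertainty about the level to expect there with a 10- or 11.5-minute infusion.

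These sizes rest on first-order decay at the stated half-life and apply to the infused part of the level only. The actual distortion cannot be established without recorded draw times. The endpoint is exploratory and descriptive, so the importance is low: worth correcting because it is cheap, not because any main conclusion depends on it.

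**What to change.** **SAP 10.7.4.** Make an exception to the scheduled-time rule of SAP 10.1. List and plot each PACAP-38 level against actual minutes since the end of infusion, and summarise by arm on that time scale. Use recorded draw times and the infusion stop times already captured on the eCRF. Show the actual draw minutes by arm beside the summary; this would also show whether timing differed between arms.

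**Time zero.** State whether 0.25 h and 0.5 h run from the start or the end of infusion.

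**Protocol 7.2.4.** Clarify whether the order applies to PACAP-38 plasma. I would not move the blood draw ahead of vital signs: challenge-day blood pressure and heart rate feed the PACAP-38 stopping rules in Protocol 6.3.1.3, and an exploratory level does not justify that trade.

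**Cost.** Recording of draw times if not already done, a few sentences of text, and slightly more analysis work. The laboratory manual and Amendment 4 should be checked first so that the wording agrees. Draw times that were never recorded cannot be recovered by the SAP change; in that case the 0.25 h summary should carry a caution.

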7.2.5 Safety Follow-up Visits/End of Study Visit/Early Termination

Subjects will return to the clinic for follow-up visits in accordance with the Schedule of Assessments (Section 7.1) and be followed through the completion of the EOS procedures. If an EOS test result demonstrates a clinically significant clinical or laboratory abnormality, the subject will be followed until resolution of the abnormality or

until it is considered clinically stable by the investigator. Subjects who terminate early will be asked to return to the research facility for the EOS assessments.

7.2.6 Medical History

The Investigator or designee will collect a complete medical history. Medical history will include information on the subject's concurrent medical conditions. Record all findings on the medical history eCRF.

7.2.7 Adverse Event

Adverse event and serious adverse event assessments will be made throughout the study and will be evaluated and recorded in the source documents and on the eCRF for the duration of the study. Determination of the severity of all adverse events will be consistent with CTCAE Version 4.0 unless specified otherwise.

7.2.8 Concomitant Medications

Concomitant medication(s) will be recorded throughout the study in the source documents and eCRF. Sites will collect therapy name, indication, dose, unit, frequency, route, and start and stop dates for all concomitant medications.

7.2.9 Physical Examination

A physical examination will be performed by the investigator or designated physician at time points specified in the Schedule of Assessments (Table 2 and Table 3). Pre-Dose abnormal findings will be reported on the medical history eCRF. Abnormal findings found after the subject has received study medication will be reported on the Adverse Event eCRF.

7.2.10 Vital Signs

The following measurements must be performed: systolic/diastolic blood pressure, heart rate, respiratory rate, and temperature. The position selected for a subject should be the same that is used throughout the study and documented on the vital sign eCRF. Record all measurements on the vital signs eCRF. The temperature location selected for a subject should be the same that is used throughout the study and documented on the vital signs eCRF. Rectal temperature will be collected at the time points designated in Table 2 and Table 3. Vital signs (blood pressure, heart rate, respiratory rate, and temperature) will be recorded by the principal investigator or designee at time points specified in the Schedule of Assessments (Table 2 and Table 3).

Blood pressure will be measured in the following manner:

- Subjects should be lying in a semi-recumbent position quietly and comfortably for at least 5 minutes. The upper arm should be bare without constrictive clothing and supported at heart level.
- Three consecutive measurements separated by approximately 5 minutes must be taken to establish baseline (ie, pre-dose) systolic/diastolic blood pressure. The mean of the three measurements should be recorded.
- Any clinically significant decrease in blood pressure readings must be confirmed with three consecutive measurements taken approximately 5 minutes apart. The mean of the three measurements should be recorded.
- Caffeine and exercise should be avoided for at least 30 minutes prior to measurement.
- An appropriately sized cuff (cuff bladder encircling at least 80 percent of the arm) should be used to ensure accuracy. At least 2 measurements should be made and the average recorded.
- Neither the subject nor the observer (measurer) should talk during measurement.

Subjects should be lying in a semi-recumbent position quietly and comfortably for at least 5 minutes for respiration and heart rate assessments. Respiration will be assessed by a full minute count. Abnormal measurements may be repeated upon investigator discretion. Record all measurements on the vital signs eCRF.

